## 1.1 Protocol Synopsis

TITLE	A multi-center, North American, open-label extension study of pridopidine (ACR16) in the symptomatic treatment of Huntington’s disease (Open-HART).
PHASE	II
OBJECTIVES	
The objective is to assess the long-term safety of pridopidine and to analyze treatment effects during long-term, open-label treatment.
 
The primary objective is to assess the long-term safety of pridopidine treatment and to collect information on UHDRS development during long-term, open-label treatment.
 
The exploratory objective is to evaluate patient and site staff satisfaction with virtual study visits and remote assessments administered in adult patients with Huntington’s disease (HD).

STUDY DURATION	
The study will continue until:
 
 
the investigational medicinal product (IMP) has been authorized for marketing by the respective regulatory authority in Canada or the USA; or
 
the study is discontinued for medical/scientific (risk-benefit) or commercial reasons.
 

STUDY DESIGN	Multi-center, open-label study of pridopidine 45 mg bid for patients who completed the HART (ACR16C009) or PRIDE-HD (TV7820-CNS-20002) studies and who transitioned from the Open-HART pre-virtualization study period.
NUMBER OF PATIENTS	47
INCLUSION AND EXCLUSION CRITERIA	
Inclusion criteria
 
 
Patient is able to and has provided written Informed Consent prior to all study-related procedures.
 
[Revision 1] Patient has completed the HART (ACR16C009) or the PRIDE-HD (TV7820-CNS-20002) studies and had remained on IMP during the full on-treatment part of the study (including de-escalated patients) or has transitioned from the Open-HART pre-virtualization study period.
 
Patient is willing and able to take oral medication and able to comply with the study specific procedures.
 
Patient is not participating in another clinical study of an investigational intervention.
 
[New criterion] Patient has a wireless internet connection at home (and/or applicable locations) at the first remote visit.
 
[New criterion] Patient has the ability to transition from in-person study visits to virtual study visits. The first remote visit will take place within approximately 30 days after the last in-person visit.
 
 
Exclusion criteria
 
 
[Revision 1] Ongoing treatment with tetrabenazine or deutetrabenazine, seizure threshold lowering medications,
 

	
or certain antipsychotics and antidepressants (see Protocol Section 5.7 and current Operations Manual for list of disallowed medications).
 

• [Revision 2] Newly instigated or changed treatment with neuroleptics/anti-psychotics.

• [Revision 3] Use of tricyclic antidepressants or class I & III antiarrhythmics at any time during the study period.

• [Revision 4] Any clinically significant, abnormal laboratory result, including clinically significant hepatic or renal impairment, or any ongoing adverse event (AE) that, in the opinion of the investigator (or qualified designee), affects the patient's suitability for the study or puts the patient at risk if he/she continues in the study.

• [Revision 5] A prolonged QTc interval at the first remote visit (defined as a QTcF interval of >450 ms for both males and females using Fredericia's formula) or other clinically significant heart conditions as judged by the investigator (or qualified designee).

• [Revision 6] Severe intercurrent illness that, in the opinion of the investigator (or qualified designee), may put the patient at risk when continuing participation in the study.

• [Revision 7] Alcohol and/or drug abuse as defined by Diagnostic and Statistical Manual - Fourth Edition - Text Revision criteria for substance abuse - this includes the illicit use of cannabis.

• Patients with AEs of suicidal ideation or attempt at any time in the past or as measured by a suicide ideation score of <math>\geq 3</math> on the Columbia-Suicide Severity Rating Scale (C-SSRS) (who answer "Yes" to questions 3, 4, and 5 in the scale suicidal ideation section), or a score of <math>\geq 3</math> on the Problem Behaviors Assessment - Short Form (PBA-s), or patients who answer "Yes" on any of the 5 C-SSRS Suicidal Behavior Items (actual attempt, interrupted attempt, aborted attempt, preparatory acts, or behavior), if an attempt or acts were performed at any time in the past, or patients who, in the opinion of the investigator (or qualified designee), present a risk of suicide.

• Patients with a known history of epilepsy or a history of febrile seizure(s) or seizure(s) of unknown cause.

• Females who are pregnant or lactating.

• Females who are of child-bearing potential and not taking adequate contraceptive precautions (either oral, barrier, or chemical contraceptives) are excluded from the study. Females of child bearing potential taking acceptable contraceptive precautions can be included.

• Known allergy to any ingredients of the study medication (Please refer to the Investigator Brochure (IB) for a full ingredient list).

• [Revision 8] Creatinine clearance <math>< 60</math> mL/min at Virtual Transition Visit (VTV), calculated using the Cockcroft-Gault equation: <math>(140 - \text{age}) \times \text{mass (kg)} \times [0.85 \text{ if female}] / 72 \times \text{serum creatinine (mg/dL)}</math>. It is allowed to repeat the test once, if clinically appropriate.

--	--

TREATMENT:	Pridopidine 45 mg twice daily (bid) – two active 45 mg capsules taken as two separate doses (90 mg pridopidine per day).
ADMINISTRATION	Oral. Capsules will be swallowed whole with water. One capsule should be taken early in the morning and one in the afternoon 7 to 10 hours after the morning dose, irrespective of food. Dose frequency de-escalation to one morning capsule only is permitted if tolerability issues arise. Subsequent re-escalation to twice-daily dosing may take place.
PROCEDURE	
The signing of informed consent and the VTV will be held at the time of the patient’s last in-person Open-HART study visit and within 30 days prior to the first remote visit (RV1). Patients may not transition from in-person visits to remote visits before signing informed consent.
 
After signing informed consent and confirmation of the ability to perform virtual study visits, patients will transition from in-person study visits to remote visits in the Open-HART study.
 
During the VTV the patient will be asked to appoint a research proxy (see Section 9.2).
 
IMP will be dispensed at the VTV. All subsequent IMP dispensation will be shipped directly to the patient.
 
Investigators (or qualified designees) will be trained on video conferencing equipment and remote connection techniques for administration of assessments prior to the patient’s first test connection. Patients will be provided with a tablet for remote video conferencing visits after they have completed their last in-person visit and provided written informed consent. A test connection will be completed at the patient’s home (and/or applicable location) by the vendor prior to the first remote visit to ensure that the investigational site and patient video conferencing equipment are working properly.
 
The first remote visit (RV1) is to be completed within 30 days of the VTV. This visit will be the first virtual visit of the study and will be completed via a remote video conference. Safety and tolerability will be assessed at all visits of treatment until the end of patient participation, including the follow-up and End-of-Study (EOS) visits. Assessments will be performed according to Section 1.3.
 
Additional remote video visits will be performed at Weeks 26, 52, and every 26 weeks thereafter (as well as for unscheduled visits [USVs]) until study discontinuation. During these virtual visits, inquiries about AEs, concomitant medication (including changes in use of benzodiazepines and antidepressants), changes in use of alcohol and drugs associated with substance abuse (legal or illicit), an evaluation for research study consent, C-SSRS collection, abbreviated PBA-s collection, and

	
the Unified Huntington's Disease Rating Scale (UHDRS) will be conducted by the investigator (or qualified designee). The UHDRS will only be collected at virtual visits every 52 weeks and at EOS/ET or USVs. The abbreviated PBA-s will be collected at visits when the UHDRS (Behavior) is not collected.
 
Remote video visits will be accompanied by an in-person visit from a mobile nurse (within 7 days). Mobile nurses will perform safety laboratory tests, pregnancy tests, vital sign measurements, electrocardiograms, weight, and study drug accountability at the patient's residence (and/or other applicable location) at the time points listed in Section 1.3.
 
Safety evaluation telephone contacts (TCs) will be conducted by the investigator (or qualified designee) between remote visits at Weeks 13, 39, 65, 91, and every 13 weeks thereafter as well as at unscheduled visits (USVs). During these TCs, inquiries about AEs, concomitant medications (including changes in use of benzodiazepines and antidepressants), changes in use of alcohol and drugs associated with substance abuse (legal or illicit), an evaluation for research study consent, C-SSRS collection, and an abbreviated PBA-s collection will be conducted by the investigator (or qualified designee). The investigator (or qualified designee) will also discuss study drug compliance with the patient during each TC. Assessments will be collected according to Section 1.3.
 
Patients who discontinue IMP due to safety or tolerability reasons, or the inability to complete virtual visits, may remain enrolled in the study without treatment at the discretion of the investigator (or qualified designee). Patients should complete the end-of-treatment (EOT) visit and continue with scheduled visits and assessments until the EOS or early termination (ET).
 
Patients who complete all scheduled visits (remote video and TC) will have procedures and assessments performed via remote video conference and mobile nurse visit at the EOS/ET visit. Patients who withdraw from the study before completing the treatment period will have the EOS visit (or ET) procedures and assessments performed at his/her final visit.
 
The end of study is defined as the last visit of the last patient.
 
All patients will be followed for safety via TCs.
 
Withdrawal from treatment If the patient wishes to stop treatment, is judged by the investigator (or qualified designee) to not be suitable for continued therapy, or the study is discontinued, a remote visit ("withdrawal visit", ET visit) should be performed and the patient withdrawn from the study. A (telephone) follow-up visit (30 d TC follow-up) to collect and report AEs, concomitant

--	---

	
medications (as well as inquiry about changes in use of benzodiazepines and antidepressants), changes in use of alcohol and drugs associated with substance abuse (legal or illicit), C-SSRS, and an abbreviated PBA-s assessment should take place 1 month after the actual discontinuation of IMP took place.
 
Additional criteria for discontinuation of IMP for individual patients are detailed in Section 7.7.1.
 
Patients who discontinue IMP due to safety or tolerability reasons may continue in the study off-IMP and perform the scheduled visits and assessments.
 
Unscheduled visits may occur as needed and can be completed via remote video, in-person visit, or TC (TC will be the primary form of contact; remote video or in-person visits may be scheduled at the discretion of the investigator [or qualified designee]). An USV may be used to perform assessments per the investigator's (or qualified designee's) judgement. An USV may also be used to re-consent a patient if necessary.
 
If patients have concerns about the virtual nature of site visits, they may request an USV at the investigational center. The medical monitor will review individual requests and may approve 1 site USV per patient, per year. The assessments at site USVs will mirror those obtained during safety evaluation TCs (see Section 4.6.4). The investigator (or qualified designee) may schedule additional site visits on a case-by-case basis for patients that require closer monitoring due to safety events.
 
If a patient has tolerability problems or has to de-escalate the investigational treatment, the investigator (or qualified designee) can decide to call the patient to an unscheduled study visit at the investigational center. Patients should be advised that if tolerability problems continue, then they should contact their investigator (or qualified designee) who may then withdraw them from the IMP (EOT visit) (see Section 7.7.2).
 
If a patient attends an USV between the scheduled visits, they should be instructed to attend their next visit according to the study schedule as planned.
 
The study will be carried out in accordance with the study protocol, guidelines on the International Conference of Harmonization for Good Clinical Practice, appropriate Food and Drug Administration Code of Federal Regulations, and local regulatory requirements.
 
During the conduct of this study, an Internal Safety Committee will review accumulating safety data on a quarterly basis (or

--	--

	
meet ad-hoc if a safety concern arises, as detailed in the Internal Safety Committee charter), to ensure the continuing safety of the study patients and study conduct issues.
 
Patients excluded from the study due to lack of internet connection or inability to transition from in-person study visits to virtual study visits may be eligible to enroll in the Open-PRIDE-HD study (Study TV7820-CNS-20016).

STATISTICS	
All reported adverse drug reactions will be tabulated. Safety statistics will be descriptive only.

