### 2.3 Rationale for Dosage Used

Patients entering this study were treated with either 0 (placebo), 10, 22.5 or 45 mg pridopidine bid in the HART study, or 0 (placebo), 45, 67.5, 90, or 112.5 mg pridopidine bid in the PRIDE-HD study.

The proposed dose selected for this study is pridopidine 45 mg bid. The proposed dose has been evaluated in 3 large HD clinical studies (HART, MermaiHD, and PRIDE-HD) as well as 2 open-label extension studies (Open-HART and Open-PRIDE-HD) and has been generally well tolerated. In PRIDE-HD, 45 mg bid was the lowest of 4 doses evaluated. [REDACTED]

[REDACTED] Thus, from a benefit-risk perspective, the Sponsor sees no benefit in continuing to explore doses higher than 45 mg bid. [REDACTED]

[REDACTED] Thus, the Sponsor sees no therapeutic benefit at exploring doses lower than 45 mg bid.

Both pharmacokinetic data and clear dose-dependent and exposure-dependent QTc findings in PRIDE-HD rule out systematic dosing errors. While the HART and MermaiHD studies had explored the clinical profile of doses up to 45 mg bid, PRIDE-HD was designed to test the high end of exposure on potential clinical benefit (Food and Drug Administration [FDA] Type C meeting; 24 July 2013).

The integrated safety analysis and large safety database from the double-blind, placebo-controlled HART, MermaiHD, and PRIDE-HD studies indicated that the AE profile of pridopidine 45 mg bid is generally well tolerated and comparable with placebo. [REDACTED]

The integrated analysis of data from the double-blind, placebo-controlled HART, MermaiHD, and PRIDE-HD studies indicated the following:

- [REDACTED]
- [REDACTED]
- [REDACTED]
- [REDACTED]
- [REDACTED]
- [REDACTED]

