#### **4.4 Inclusion Criteria**

- Patient is able to and has provided written Informed Consent prior to all study-related procedures.
- [Revision 1] Patient has completed the HART (ACR16C009) or the PRIDE-HD (TV7820-CNS-20002) studies and had remained on IMP during the full on-treatment part of the study (including de-escalated patients) or has transitioned from the Open-HART pre-virtualization study period.
- Patient is willing and able to take oral medication and able to comply with the study specific procedures.
- Patient is not participating in another clinical study of an investigational intervention.

- [New criterion] Patient has a wireless internet connection at home (and/or applicable locations) at the first remote visit.
- [New criterion] Patient has the ability to transition from in-person study visits to virtual study visits. The first remote visit (RV1) will take place within approximately 30 days after the last in-person visit.

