## **8.8 Efficacy Set**

Descriptive statistics of each of the efficacy variables for the efficacy analysis set will be presented by yearly intervals. Changes in efficacy parameters will be calculated both from baseline (in main study) and from start of this extension part.

The efficacy parameters will also be presented graphically.

Efficacy data will be presented for all patients combined.

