### **8.9.2 Adverse Events**

All AEs starting either after the first dose and until 2 weeks after the last dose (scheduled follow-up period) in Open-HART, or Open-PRIDE-HD and continuing in the virtualized Open-HART or starting after the first dose in the Open-HART virtualization will be reported and regarded as treatment-emergent.

Separate displays will be presented for events starting in the Open-HART virtualization. In these displays, only an overall pridopidine treatment group will be presented. Both crude incidences and incidence rates (patients with events per exposure) will be presented.

Combined AEs from HART and Open-HART (ACR16C009 and ACR16C015, respectively) will be reported through an Integrated Summary of Safety.

The following displays will be generated:

- A brief summary of AEs will be tabulated.
- AEs will be summarized by system organ class and preferred term, severity, and relationship to IMP.
- Separate displays of SAEs and AEs leading to discontinuation will be produced.
- All AEs will be listed.

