### **4.2. Specification of Baseline Values**

The baseline value is the last observed data prior to the first dose of study drug in this study.

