## **6. EFFICACY ANALYSIS**

### **6.1. General**

The full analysis set analysis set will be used for all study population summaries unless otherwise noted. Summaries will be presented for all patients.

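### The SAP pools patients from parent-study placebo with patients from pridopidine arms, so QTcF change, early AEs and first-year UHDRS change mix first exposure with step-up, continuation and step-down

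*Protocol*

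**What the plan says.** **What the study sets out to do.** Protocol 1.1: "The objective is to assess the long-term safety of pridopidine and to analyze treatment effects during long-term, open-label treatment". SAP 1 repeats this sentence.

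**Who enters.** Protocol 2.3: "Patients entering this study were treated with either 0 (placebo), 10, 22.5 or 45 mg pridopidine bid in the HART study". For PRIDE-HD the same section lists placebo and four active doses: 45, 67.5, 90 and 112.5 mg bid. Protocol 4.4 requires that parent-study completers "had remained on IMP during the full on-treatment part of the study (including de-escalated patients"); SAP 2.5 likewise enrols completers of either parent study. All are then assigned 45 mg bid (Protocol 5.1, SAP 2.1).

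**Which baseline.** SAP 4.2: "The baseline value is the last observed data prior to the first dose of study drug in this study". SAP 6.2, 7.4 and 7.5 all work with changes from baseline.

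**Which grouping.** SAP 6.1, on efficacy: "Summaries will be presented for all patients". SAP 5.1 (study population) and SAP 7.1 (safety) use the same sentence. Protocol 8.8 agrees: "Efficacy data will be presented for all patients combined". Parent arm is not among the baseline characteristics in SAP 5.3 and is not a subgroup or column anywhere in the SAP.

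**Which version governs.** SAP 2.1 says the SAP follows Protocol Amendment 04 and that Amendment 05 was not implemented. The protocol text available here is Amendment 05, so the point rests on the SAP. The SAP also states that it prevails where the two differ.

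**The concern.** A change score means different things depending on what the patient was taking before its baseline. For a patient coming from placebo, the change from extension baseline includes the effect of starting pridopidine. For a patient coming from 45 mg bid without a long gap, it reflects continuation. For a patient from 10 or 22.5 mg bid it reflects a step up, and for one from 67.5, 90 or 112.5 mg bid a step down. One pooled mean or count describes none of these groups.

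Three outputs are exposed:
- **QTcF change (SAP 7.5), including the counts above 30 and above 60.** This is the clearest case, because Protocol 2.3 itself reports QTc findings in PRIDE-HD that depend on dose and exposure. Patients stepping down could start from a raised value, patients from placebo from an unexposed one, and the two changes would then run in opposite directions.
- **Early AEs (SAP 7.3).** Patients from active arms have already stayed on drug through a parent study. Patients from placebo have not been tested on it.
- **UHDRS change at the first annual visit (SAP 6.2).**

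At stake is whether a reader of the study report can tell what happens when pridopidine is started from what happens when it is continued.

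**Working it through.** The plan gives no sample-size, power or dilution figure to reproduce. It does not give the number of patients from placebo, the parent allocation ratios or the gap between parent study and extension. What follows is illustration under declared assumptions.

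**Inputs from the documents.** HART has 4 arms (0, 10, 22.5, 45 mg bid). PRIDE-HD has 5 arms (0, 45, 67.5, 90, 112.5 mg bid). The extension dose is 45 mg bid.

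**Assumptions.** Equal allocation, proportional roll-over, no off-drug gap. The share w from placebo is then 1/4 = 25% (HART) or 1/5 = 20% (PRIDE-HD).

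**1. Share of the 45 mg bid effect not yet in the baseline, averaged over arms**
- All active arms already carry the full effect. HART: (1 + 0 + 0 + 0)/4 = 25%. PRIDE-HD: (1 + 0 + 0 + 0 + 0)/5 = 20%.
- HART, effect proportional to dose: (1 + (1 - 10/45) + (1 - 22.5/45) + 0)/4 = (1 + 0.778 + 0.5 + 0)/4 = 57%.
- HART, no effect below 45 mg bid: (1 + 1 + 1 + 0)/4 = 75%.
- Under the full-effect assumption the pooled share equals w, so it runs from 10% to 50% if w runs from 0.10 to 0.50.
- With complete washout before entry the share is 100% in every group and there is no dilution.

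For UHDRS these shares apply only to the drug component. A one-year change also contains disease progression in every group.

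**2. QTcF among PRIDE-HD entrants.** If the effect were strictly proportional to dose, the expected change on moving to 45 mg bid, in units of the 45 mg bid effect, would be 1 - (parent dose)/45:
- placebo: +1
- 45 mg bid: 0
- 67.5 mg bid: -0.5
- 90 mg bid: -1
- 112.5 mg bid: -1.5

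The mean is (1 + 0 - 0.5 - 1 - 1.5)/5 = -0.4. The pooled mean would fall while new starters rose by a full unit. SAP 2.1 schedules the Month 1 ECG only for patients from PRIDE-HD, so the earliest scheduled QTcF summary would consist of this mix.

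**3. Early AEs.** Pooled risk = w x (risk in new starters) + (1 - w) x (risk in others). With assumed risks of 30% and 10%:
- w = 0.20: 6 + 8 = 14%
- w = 0.25: 7.5 + 7.5 = 15%
- w = 0.10 and 0.50: 12% and 20%

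If the two risks are equal, for example 20% and 20%, the pooled value is 20% and nothing is lost.

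**4. Precision of a prior-placebo column.** With zero events in n patients, the one-sided 95% upper bound is 1 - 0.05^(1/n): 45% for n = 5, 22% for n = 12, 12% for n = 24. These sizes are arbitrary; the actual number is not in the documents.

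**The case against.** **The study never set out to estimate a first-exposure effect.** The primary objective is long-term safety and collecting UHDRS information. SAP 6.2 calls efficacy exploratory and applies no inference, Protocol 6.1 leaves efficacy assessment to the sponsor, and first exposure was studied in the placebo-controlled parent trials. This stands. The pooling does not make the study fail its objectives; it makes some outputs harder to read.

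**Existing outputs help in part.** SAP 7.3 already plans AEs by time period, though pooled and with the periods undefined. The absolute QTcF counts (above 450, 480 and 500 ms) do not depend on baseline. Protocol 8.8 also plans change from the main-study baseline, which for active-arm patients precedes parent-study exposure, but SAP 6.2 does not carry it over.

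**A reader might infer more than the documents support:**
- *That patients from active arms had already responded, or were still on drug at entry.* Entry requires completing the parent study on study medication, not responding. The gap is not given, and SAP 2.1 describes a fresh baseline visit, a Week 1 call and a Month 1 visit.
- *That new AEs on starting can arise only in patients from placebo.* Patients from 10 or 22.5 mg bid step up, and anyone restarting after a gap starts afresh.
- *That Protocol 8.9.2 proves the pooling, because "only an overall pridopidine treatment group will be presented".* That wording covers only displays for the virtualised part, which was not implemented.
- *That the number from placebo follows from the 47 patients in the synopsis.* That figure belongs to Amendment 05 and is not the SAP's denominator.
- *That splitting by parent arm restores a randomised comparison.* Both groups are parent-study completers, and there is no concurrent untreated control.

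**Conclusion.** The concern holds as a matter of interpretability. Entrants have mixed prior exposure, the SAP's baseline ignores it, and no planned SAP output separates it. The consequence is most direct for QTcF change, where the protocol itself reports dose dependence and where step-down and first exposure could offset each other. It applies also to early AEs and first-year UHDRS change.

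The size is unknown. The 20-25% figure requires equal allocation, proportional roll-over, no washout and a full effect already present in every active arm. Lower parent doses carrying less effect, or an off-drug gap, would make the dilution smaller. The direction for AEs requires that risk differs by prior exposure. This is a worthwhile, inexpensive improvement that should be made before database lock.

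**What to change.** - In SAP 6.2, 7.3 and 7.5, keep the pooled column and add two descriptive columns by parent-study randomised treatment: prior placebo and prior pridopidine. Apply them to UHDRS change at the first annual visit, AEs by time period (periods defined, the first shown separately) and QTcF change including the above-30 and above-60 counts.
- In SAP 5.3, add parent study, parent arm and the interval between the last parent-study dose and the first dose here. The interval tells the reader how much weight the split deserves, and parent arm shows the dose mix inside the prior-pridopidine column.
- Use no tests. State that both groups are parent-study completers and that the split is descriptive, not a randomised contrast.

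**Cost.** SAP wording and extra table columns. No new assessments are needed: Protocol 4.2 gives each patient a cross-study identifier and SAP 5.3 already draws on parent-study baseline data. The prior-placebo column will be small and imprecise, and the prior-pridopidine column still spans 10 to 112.5 mg bid, so both need cautious reading.
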